Based on audits of our *Registry* data, we expect <1% missing data for the following key elements: institution, sex, ethnicity, gestational age at birth, delivery mode, Apgar scores, hypothermia treatment, indication for EEG, seizure type, primary seizure etiology, disposition and seizure medication prescribed at the time of discharge. For Aims 1 and 3, in our study design we have conservatively accounted for 15% loss to follow-up (the anticipated main source of missing data) and have adjusted our enrollment target accordingly. We will perform sensitivity analyses to assess the potential impact of loss to follow-up: we have extensive information about our participants and will compare those that are and are not lost to follow-up. We will compare our primary analysis (a complete case analysis) with an analysis using multiple imputation using the "multiple imputation with chained equations" methodology. This approach allows us to specify realistic models for each variable, such as the ordered categorical for the Engel scale. For Aim 2, we expect little to no missing data. Also, for Aim 3, we will audit the amount of missing data for the open-ended free-text questions to determine if there are patterns and will consult with our Parent Partners about ways to improve response rates if needed.

Heterogeneity of treatment effects [HT-1 to 4]. As suggested by PCORI methodological guidelines, all assessments of heterogeneity of the effect of short versus prolonged phenobarbital treatment have been preplanned and have been justified (see *Potential participant subgroups* section below). Analysis will be by entering subgroup by intervention interaction effects in the analyses described above to test for moderation.

Reporting plan [IR-6]. Data will be reported according to STROBE (Strengthening the Reporting of Observational studies in Epidemiology) guidelines, as is recommended for observational studies.

Patient-centered outcomes research (PCOR) data registry details are presented in Appendix 6.

D. Project Milestones and Timeline

Table 3: Project Timeline

	Months					
	1-6	7-12	13-18	19-24	25-30	31-36
Planning						
- Finalize protocol	\checkmark					
- IRB approval	\checkmark					
 Clinicaltrials.gov registration & results reporting 	~					\checkmark
Patient Enrollment						
- Start recruitment		\checkmark				
- Complete 25% recruitment		\checkmark				
- Complete 50% recruitment			✓			
- Complete 75% recruitment			✓			
- Complete enrollment				~		

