Neonatal seizures affect boys slightly more often than girls (*Neonatal Seizure Registry* data: 55% male, 45% female), but children of all races and ethnicities are affected. Among the *Neonatal Seizure Registry's* subjects, the distribution of race/ethnicity is similar to the American pediatric population. We anticipate a similar distribution for the proposed follow-up study, which will be representative of American children.

Inclusion of Children. All study subjects will be children.

Potential participant subgroups [RQ-4; HT-1 to 4].

Our study is powered to evaluate the primary outcome (development at 24 months) across a wide-ranging population of neonates with seizures. This will improve generalizability. We will also have an opportunity to perform exploratory secondary analyses for some subgroups:

- EEG confirmed vs. clinically diagnosed neonatal seizures: Although all *Neonatal Seizure Registry* sites conform to the ACNS Guidelines for neonatal EEG monitoring³⁸, there are occasions in which an at-risk infant's clinical events resolve prior to the initiation of EEG. In the proper clinical context, many such newborns are treated empirically with anticonvulsant medications. In two small studies, the risk for subsequent epilepsy was higher among infants with EEG-confirmed neonatal seizures than those with clinically diagnosed seizures^{3,39}. Therefore, we will evaluate for differences in 24-month outcomes between those with clinical versus EEG-confirmed seizures.

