Possible biases due to differential loss to follow-up: It is possible that infants who are discharged from the initial hospital admission *without* anticonvulsant medication will be more likely to be lost to follow-up, since they will not need to present to a neurology clinic for prescription medication refills. In our clinical experience, however, these families want to return to clinic at least at the 2-4 month time point, so that a specialist can evaluate their child's growth and development. If a child is doing well, families who live farther from the study site may be less likely to follow-up at later time points. We have designed the assessment to avoid this problem by utilizing telephone interviews, online and mailed surveys. Even for families who do not complete the assessments, the medical chart can be reviewed. In cases where a family cannot be reached by telephone, a diagnosis of epilepsy will be readily apparent from electronic medical record review.

Data Safety and Security: Local Institutional Review Boards approvals for the *Neonatal Seizure Registry Sites* will be amended to reflect changes to the study design. Data will be collected using REDCap, an online, HIPAA compliant database that is designed for use in health care. Data will be de-identified, with each site maintaining local record of the patient medical record number in a secure manner (either on an encrypted and password protected computer that is maintained in a locked room, or paper file that is maintained in a locked cabinet in a locked room). Data that were collected for the *Neonatal Seizure Registry* prior to initiation of this proposal will be used only following informed consent from families.

Informed Consent: A study investigator will contact the parents/legal guardians of eligible patients and, using a consent form approved by the local Committee on Human Research (Institutional Review Board), describe the known risks and benefits of the study. The consent teams will include only experienced study personnel who are sensitive to the vulnerable nature of this population and who will emphasize the voluntary nature of research.

Data Quality Assurance

Data will be collected and entered into a REDCap database according to policies established for the *Neonatal Seizure Registry*.

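### Complete case is primary for Aim 1a although the plan names a route to biased loss; imputation using the earlier WIDEA scores should lead instead

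*Combined protocol and SAP*

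**What the plan says.** All of this is in the combined protocol and SAP.

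- **Primary analysis (Missing data [MD-1 to 5]).** "We will compare our primary analysis (a complete case analysis) with an analysis using multiple imputation". The imputation uses chained equations and follows the sentence "We will perform sensitivity analyses to assess the potential impact of loss to follow-up", so its role is secondary. Of the method the section says "This approach allows us to specify realistic models for each variable, such as the ordered categorical for the Engel scale". It lists no predictors and does not say which result decides if the two differ.
- **Loss mechanisms (Appendix 6, Possible biases due to differential loss to follow-up).** Infants discharged without anticonvulsant medication are named, as a possibility, as a group that "will be more likely to be lost to follow-up, since they will not need to present to a neurology clinic for prescription medication refills". The second mechanism reads: "If a child is doing well, families who live farther from the study site may be less likely to follow-up at later time points".
- **Mitigation (same paragraph).** "We have designed the assessment to avoid this problem by utilizing telephone interviews, online and mailed surveys". Chart review is the back-up, but the only result it is said to make apparent is an epilepsy diagnosis.
- **Outcome timing.** Aim 1 schedules the WIDEA FS at 12, 18 and 24 months. Potential participant subgroups identifies the primary outcome as development at 24 months.
- **Size of loss.** Missing data and Appendix 6 allow 15%. One sentence under Sample Size Calculations, Aim 1a, raises this to 20%. No rate is given by treatment group.

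**The concern.** A complete-case comparison is sound if, within each group and given the adjustment covariates, retained children are like lost ones. Appendix 6 gives a reason to doubt that: one mechanism makes loss heavier in the short group, the other makes it heavier among children doing well. If both act, the short group loses more of its better scorers and looks worse than it is.

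The propensity score is built from neonatal and discharge variables. It cannot carry how the child is doing at 12 or 18 months, which is what the second mechanism turns on. The repeated WIDEA scores do carry that information, but the plan gives them no role in either the primary model or the imputation model.

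At stake is the non-inferiority conclusion for short duration, which would rest on the analysis more exposed to this bias, with no rule for a disagreement.

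**Working it through.** **Inputs from the documents.** SD 16.5 (12-month WIDEA); margin 7 with a one-sided 95% limit; 80% power; N = 192; groups 90 and 210; propensity inflation 9%; loss 15% or 20%; 24-month margin 4.25, written as a percentage and read here as points. The 24-month SD is not given.

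**Assumptions.** Loss 25% short / 10.7% prolonged (0.3 × 25 + 0.7 × 10.7 = 15.0% overall) or 30% / 12% (17.4% overall). Odds of loss double per SD of better 18-month score in both groups. Correlation r of the 18- and 24-month scores is 0.6 to 0.8. There are no covariates and no true difference. The 24-month SD is taken as 16.5 × 4.25/7 = 10.0.

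**1. The plan's own figure.** N = (1.645 + 0.842)² × (16.5/7)² × (1/f + 1/(1-f)), with f the short share. At the registry's 23:77 split this is 194.0 (45 + 151 = 196 after rounding). At 30:70 it is 163.6, and 163.6/0.85 = 192.4. Either route could be the source of 192, which is not in dispute. With the allowances, 192 × 1.09/0.85 = 246 and 192 × 1.09/0.80 = 262, both under 300. This headroom protects precision and does nothing about bias.

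**2. Loss that differs by group only** (odds ratio 1): bias is 0 at any split.

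**3. Both mechanisms acting.** Bias (short minus prolonged) = r × SD × (m_S - m_P), where m is the mean standardised 18-month score among retained children under logistic loss. Numerical integration gives m = -0.1595 at 25% loss, -0.0707 at 10.7%, -0.1899 at 30% and -0.0789 at 12%.

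| Loss short / prolonged | m_S - m_P | r | Bias, SD 16.5 | Share of 7 | Bias, SD 10 | Share of 4.25 |
|---|---|---|---|---|---|---|
| 25% / 10.7% | -0.0888 | 0.6 | -0.88 | 13% | -0.53 | 12-13% |
| 25% / 10.7% | -0.0888 | 0.8 | -1.17 | 17% | -0.71 | 17% |
| 30% / 12% | -0.1110 | 0.6 | -1.10 | 16% | -0.67 | 16% |
| 30% / 12% | -0.1110 | 0.8 | -1.46 | 21% | -0.89 | 21% |

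**4. Effect on the test.** After 15% loss and the 9% inflation, the effective groups are 90 × 0.85/1.09 = 70.2 and 210 × 0.85/1.09 = 163.8. SE = 16.5 × √(1/70.2 + 1/163.8) = 2.35. Power at no true difference = Φ((7 + bias)/SE - 1.645): 91% with no bias, 83% at -0.9, 76% at -1.45. With SD 10 and margin 4.25 (SE 1.43): 91%, 84% at -0.5, 76% at -0.9.

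**5. What the earlier score buys.**
- Loss depends on the 18-month score and every lost child has it: bias is about 0.
- A random half of lost children lack it: each group's bias shrinks by the factor 0.5(1-p)/(1-p/2), with p its loss. At 25% / 10.7%, the factors are 0.429 and 0.472, so m_S - m_P becomes -0.0684 + 0.0334 = -0.0350, a cut of 61%. At 30% / 12% the cut is 63%.
- Loss depends on the unseen 24-month score (25% / 10.7%, SD 16.5): bias goes from about -1.5 to between -1.0 and -0.3 for r from 0.6 to 0.9.

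**The case against.** The plan's defence has substance. Appendix 6 raises both mechanisms only as possibilities, limits the second to families living farther away, and designs follow-up by telephone, online and mail to counter them. Imputation and a comparison of lost with retained children are already planned. The propensity covariates (etiology, seizure burden, discharge examination, gestational age) may explain part of any outcome-related loss, and the illustration leaves them out. No text excludes the 12- and 18-month scores from the imputation.

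Four stronger readings are tempting, and the documents do not support them:

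- **That the plan expects differential loss.** It says only that such loss may occur, and it gives no rate by group.
- **That the earlier scores are there for every child and would abolish the bias.** Half the cohort was already enrolled and chosen to be young enough for the 24-month assessment. Table 3 starts 24-month follow-up of these infants in months 7-12, the same window in which recruitment starts, so some may be past 12 or even 18 months at consent. Children lost early also have no score.
- **That the bias could reach a third of the margin.** This comes from dividing -1.46 by 4.25 (34%), which sets a 12-month SD against a 24-month margin that the plan ties to a smaller SD.
- **That the plan risks a false claim of non-inferiority.** The pattern described works against short duration. Only a reversed pattern would inflate the error (+1 point: from 5% to 11% at margin 7), and Appendix 6 does not describe one.

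What remains is that 15-20% loss is still budgeted after mitigation, nothing is said to recover a missing WIDEA, and the analysis better placed to handle the named risk has unstated predictors and no authority over the conclusion.

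**Conclusion.** The point holds as a low-cost improvement to the analysis plan. It does not show that the result will be biased. If both named mechanisms act, complete case would be off by about -0.9 to -1.45 points at SD 16.5 (13-21% of 7), or about -0.5 to -0.9 points at an assumed 24-month SD of 10 (12-21% of 4.25 read as points). Power at no true difference would fall from about 91% to 76-84%. The loss split, odds ratio, correlation, 24-month SD and absence of covariates are all assumptions. The direction depends on heavier loss in the short group combined with heavier loss among children doing well. The earlier WIDEA removes the bias only if loss depends on that score and the score is observed; otherwise it reduces it.

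**What to change.** Amend the Missing data and Aim 1 analysis text as follows.

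1. Make the primary Aim 1a analysis one of two options, reading the 24-month contrast:
   - the planned chained-equations imputation, with treatment group, the propensity covariates and the 12- and 18-month WIDEA where observed named as predictors; or
   - a likelihood-based repeated-measures model of the 12-, 18- and 24-month WIDEA with group by visit and the propensity score.
2. Keep complete case as a sensitivity analysis.
3. Add a delta-adjusted (missing-not-at-random) analysis, judged against the margin.
4. State that the new primary analysis governs the non-inferiority conclusion.

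The sample size does not change and no new data are needed, because the assessments and the imputation are already planned. The costs are slightly more analysis work, reliance on a missing-at-random assumption (which the delta adjustment probes), and incomplete earlier scores for some previously enrolled infants, which both methods can accommodate.

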Preliminary data suggest adequate heterogeneity in clinical practice to examine short *versus* **prolonged phenobarbital duration within our established multi-center registry.** Unpublished data from our *Neonatal Seizure Registry* indicate heterogeneity for neonatal seizure treatment. Among 306 consecutive newborns enrolled in the *Neonatal Seizure Registry* for acute symptomatic seizures who survived to discharge, 23% had medication discontinued prior to discharge (range by site 3 to 75%), while 77% continued on anticonvulsants. In multivariate analyses, treating institution was the only independent predictor of continued medication after *discharge to home* (p<0.001); neither seizure burden nor etiology of acute symptomatic seizures predicted this treatment decision (p>0.1). Phenobarbital was the most commonly prescribed anticonvulsant (89% of those maintained on medication).

Outcome selection [RQ-6]. Our proposed outcome measures are all highly relevant to parent stakeholders. *Primary outcome.* After discussion with Parent Partners, we selected the Warner Initial Developmental Evaluation of Adaptive and Functional Skills (WIDEA FS), a simple, free, one-page assessment that will be administered by telephone at age 12, 18, and 24 months to determine functional developmental outcome (Aim 1a).²⁰ In order to administer the WIDEA FS, the examiner (who is blinded to the treatment group) asks the parent a series of questions to determine which specific developmental milestones have been gained in the following domains: Feeding, Dressing, Diaper Awareness, Mobility, Communication, and Social Cognition. The results are tabulated and scored against norms for age for children ages 0-36 months. The WIDEA FS takes about 20-30 minutes to administer, and requires minimal training for the research team. [name] (Co-

PCORI Research Plan version 2 8/1/2016

Investigator) – a neonatologist and developmental pediatrician with extensive experience establishing neurodevelopmental outcomes from clinical trials – will oversee all aspects of the developmental outcome aim. She is trained to use and teach the WIDEA FS, and will train a research coordinator from each site to perform the measure.

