Patient Evaluation						
- Follow-up EEG (age 2-4 months) (Aim 1)		✓	\checkmark	\checkmark	\checkmark	
- 24-month follow up (Aim 1) - previous NSR subjects		\checkmark	✓	\checkmark		
- 24-month follow up (Aims 1&3) - newly enrolled subjects			\checkmark	\checkmark	\checkmark	\checkmark
Analysis						
- Interim analysis				\checkmark	✓	
- Final analysis						\checkmark
Progress reports						
- Interim progress reports	\checkmark	\checkmark	✓	\checkmark	\checkmark	
- Final progress report						\checkmark
Engagement Updates	✓	✓	✓	✓	✓	~
Dissemination						
- Write manuscripts					✓	\checkmark
 Submit copies of published manuscripts 					\checkmark	\checkmark
 Presentations by PIs/stakeholders at national meetings 					✓	\checkmark
- Write management guidelines						\checkmark
- Apply for additional funding					✓	\checkmark
- Newsletters to participating families to report results					✓	\checkmark
- Partner with Hand to Hold to disseminate results online					✓	\checkmark

E. Patient Population

Table 4: Quarterly Neonatal Seizure Registry enrollment (6/2013 to 9/2015)			
Site	Median (min, max)	Total Newborns Enrolled in NSR	
UCSF	6 (2, 13)	59	
University of Michigan	12 (5, 16)	102	
MGH	3 (0, 10)	29	

Recruitment Plan. We aim to collect follow-up information for 150 infants that have already been enrolled in the *Neonatal Seizure Registry* (from among >300 eligible newborns; a representative sample of the youngest infants at the time of study initiation will be approached for consent, to allow for prospective collection of 24-

Stanford	6 (0 , 29)	72
СИМС	10 (0, 37)	86
СНВ	11 (5, 17)	79
СНОР	2 (0, 19)	40

month outcome data). An additional prospective sample of 150 newborns will also be enrolled. We have had stable enrollment of 20-30 newborns/month, >70% of whom have acute symptomatic seizures and would meet enrollment criteria for the proposed study. Thus, we expect 250-375 eligible infants over the 18 month enrollment period. We, therefore, will need to enroll 40-60% of eligible newborns, which is very conservative for a non-intervention study with non-invasive follow-up. We will monitor enrollment monthly and address lagging rates on a site-specific basis, as necessary. Given that PCORI requests data within nine months of the end of the final year of funding, even if recruitment is slower than anticipated, there is an additional six months of recruitment time available to us to meet this deadline.

Table 5: Recruitment Goals

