Table 8: Parent Partner Advisory Panel Timeline.

				М	onths		
	Pre-submission	1-6	7-12	13-18	19-24	15-30	31-36
Planning							
- Recruit parents to the Parent Partner	\checkmark						
Advisory Panel							
 Initial and follow-up focus groups to 	\checkmark						
discuss well-being domains and select		\checkmark	✓	✓	\checkmark	\checkmark	\checkmark
validated instruments							
 Monthly telephone conferences 		\checkmark	✓	✓	\checkmark	\checkmark	\checkmark
Document Review							
- Review Manual of Operations and Case		\checkmark					
Report Forms							
Dissemination							
- Preparation of newsletter to disseminate						\checkmark	\checkmark
results							
- Presentation at society conferences						\checkmark	\checkmark
- Updates to websites (e.g. Hand to Hold)						\checkmark	\checkmark

Colearning. Parents and stakeholders have already engaged in frequent, open dialogues with the PIs regarding the study design. The PIs have been teaching the parents and other stakeholders about the scientific evidence and options of research protocol design. The PIs have participated in PCORI webinars and have discussed the project with a PCORI ambassador. The Parent Partners focus groups contained a specific educational segment on patient-centered research and PCORI.

Meanwhile, the stakeholders have been critical in informing the PIs about parents' priorities and the best assessment instruments for use in the parent and family well-being outcome assessments. Together with [name] and [name], [name] composed the parent web survey that was posted to the Hand to Hold website and inquired about families' experiences with neonatal seizures and their treatment. Data generated from that survey were critical for informing the design of this proposal.

Additional opportunities for reciprocal relationships and co-learning include:

- Monthly teleconferences for project updates and mutual decision-making.
- Development of publications and presentations for dissemination of study results to parent groups.

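### Table 3 starts sending results to participating families and the public in months 25-30, before nearly all of the 150 newly enrolled families can give their parent-reported 24-month outcome

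*Combined protocol and SAP*

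**What the plan says.** All of the following is in the combined protocol and SAP.

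- **Release of results (section D, Table 3).** Three rows are ticked in months 25-30 and 31-36: "Newsletters to participating families to report results", "Partner with Hand to Hold to disseminate results online" and "Presentations by PIs/stakeholders at national meetings". Manuscript writing has the same two ticks.
- **Analyses (Table 3).** "Interim analysis" is ticked in months 19-24 and 25-30. "Final analysis" is ticked in months 31-36 only.
- **Follow-up (Table 3).** "24-month follow up (Aims 1&3) - newly enrolled subjects" is ticked from months 13-18 through 31-36. The corresponding row for infants already in the registry ends in months 19-24.
- **Family notification (Dissemination and Implementation Potential, part C).** The newsletter to families is described under a heading about sharing results once the analyses are finished.
- **Clinicians (same section, part A).** Dissemination through society meetings is promised within a year after the study ends.
- **Table 8.** The newsletter row reads "Preparation of newsletter to disseminate" results, which is drafting rather than sending. Conference presentations and website updates are ticked in the same two columns (the earlier one is printed 15-30, apparently meaning 25-30).
- **Primary outcome (Outcome selection).** The blinded examiner "asks the parent a series of questions to determine which specific developmental milestones have been gained". The Aim 3 scales in Appendix 5 are also completed by parents.

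**The concern.** Parents know whether their child went home on phenobarbital; Appendix 4 even asks them when the medicine was stopped. Suppose families, or the network they read, are told how the short and prolonged groups compare, and are later asked to rate their child's skills and their own well-being. Their answers, and their willingness to answer at all, may then depend on what they were told. Blinding the interviewer does not protect against this, because the information reaches the person who supplies the data. Bias already built into collected reports cannot be repaired in analysis. The plan contains no rule that withholds by-group results until the last interview.

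**Working it through.** **Inputs**

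- Recruitment starts in months 7-12 and is complete in months 19-24 (Table 3). At its widest this is the start of month 7 to the end of month 24, or 6 to 24 elapsed months.
- 150 new infants over 18 months (Data Analysis).
- New infants are recruited before leaving the hospital (Overview of study design), so age at enrolment is close to zero.
- The primary outcome is development at 24 months of age (Potential participant subgroups).
- Recruitment may be extended by six months (Recruitment Plan).

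**Step 1: Table 3's printed window.** Earliest 24-month assessment: 6 + 24 = 30 elapsed months, the start of month 31. Latest: 24 + 24 = 48. The printed start of months 13-18 cannot be reproduced. An infant assessed at 24 months of age in month 18 would have been born before the study began, and so could not be newly enrolled. The printed end of month 36 is also too early.

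**Step 2: how many outcomes exist when release begins.** With uniform accrual, the number of completed 24-month interviews by elapsed month t is 150 × (t − 24 − 6)/18, bounded by 0 and 150.

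| End of month | Calculation | New families with 24-month outcome |
|---|---|---|
| 30 | 150 × 0/18 | 0 |
| 36 | 150 × 6/18 | 50 |
| 48 | 150 × 18/18 | 150 |

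**Step 3: sensitivity.**

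- If infants are about one month old at enrolment, the lag is 23 months. By month 30: 150 × (30 − 23 − 6)/18, about 8 of 150.
- With Table 3's milestone of 25% recruited by month 12, the count at month 36 is 0.25 × 150, about 38 instead of 50.
- With the six-month extension, the last interview is at 30 + 24 = month 54.
- Taking Table 3 literally, some new families are interviewed before month 25, but the months 31-36 interviews still follow the first release.

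**Step 4: the 12-month interviews.** These also collect the WIDEA FS and Aim 3 scales. By month 30, 150 × (30 − 12 − 6)/18 = 100 are done, so about 50 would still follow the start of release.

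**Step 5: what an interim analysis could contain.** Before month 31, 24-month data can come only from the 150 previously enrolled infants, whose follow-up row ends by month 24. A by-group developmental result is therefore possible in months 19-30, but the documents do not say that one is planned.

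**The case against.** The best reply is that Table 3 is weak evidence of intent. Its follow-up row is unworkable by the plan's own dates; its right-hand end fits a 12-month assessment (24 + 12 = 36) better than a 24-month one. Part C of the Dissemination section ties family notification to completed analyses, and Table 8 speaks only of preparing a newsletter. Aim 2 (length of stay) needs no follow-up after discharge, so the months 25-30 ticks could refer to Aim 2 results. Examiners are blinded, many WIDEA FS items ask about concrete behaviours, and treatment duration group is fixed at discharge, before month 25 unless recruitment is extended.

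Much of this stands. It turns the point into a conflict to be reconciled rather than proof of an intended early release. It does not remove the point, because nothing restricts the ticked releases to Aim 2 and nothing withholds by-group Aim 1 or Aim 3 results.

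Four stronger readings are tempting and are not supported:

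- **That the interim looks are unblinded group comparisons.** The only text is a row label with two ticks. Content, masking and access are not described.
- **That early results would favour non-inferiority.** The direction depends on what is released and how parents react, and the documents give no basis for either.
- **That a small shift would consume the margin.** A one-category change on four of the 50 items is 4 points, close to the 4.25 stated for 24 months. No passage supports that size, and an equal shift in both groups cancels. If half the sample is affected, a 4-point differential moves the overall contrast by about 0.5 × 4 = 2 points.
- **That the one-sided 5% error is inflated.** Applying the rule at one look with half the information and again at the end would give about 8%. That assumes non-inferiority can be declared at the interim, and the plan states no such rule.

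**Conclusion.** The point holds as a scheduling conflict with an avoidable risk to a parent-reported primary outcome. Followed as printed, Table 3 would start releasing results in months 25-30, when between 0 and about 8 of the 150 new families could have given the 24-month outcome. Essentially half of the planned 300 would be interviewed afterwards, in about months 31-48. This rests on enrolment near birth and on recruitment in months 7-24; uniform accrual affects only the intermediate counts. The exposed routes are parent reporting (WIDEA FS and Aim 3) and retention, not treatment assignment. The size and direction of any bias cannot be derived from the documents. The change is a cheap improvement; the silence about the interim analysis is missing detail, not a demonstrated error.

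**What to change.** 1. In Tables 3 and 8, move every release of by-treatment Aim 1 and Aim 3 results (to families, parent networks, meetings or journals) to after the last 24-month interview and data lock.
2. Before then, allow progress-only newsletters and, if wanted, Aim 2 length-of-stay results.
3. Correct the new-subject 24-month row to about months 31-48, and move the final analysis accordingly.
4. Reconcile Tables 3 and 8 with part C of the Dissemination section, so that one rule governs when families are told.
5. State that the months 19-30 interim analysis uses data pooled across treatment groups (recruitment, retention, pooled SD, pooled epilepsy rate), and who sees it.

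The cost is delay: by-group results appear around month 48, or 54 if recruitment is extended. That is beyond Table 3's 36 months and the three-year grant cycle in Appendix 6, so it needs planning with the funder. Most of the delay is not caused by the fix, because a complete 24-month analysis cannot exist before then on the plan's own enrolment dates. What is given up is the early circulation of partial by-group results.
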